5.2. Exclusion Criteria

Any potential participant who meets any of the following criteria prior to enrollment (consent date) will be excluded from participating in the study:

1. Criterion modified per Amendment 2
 - 1.1. currently taking an SGLT2i or within the last 3 months
2. history of diabetic ketoacidosis or have type 1 diabetes mellitus (T1DM)
3. Criterion modified per Amendment 2
 - 3.1. have acute decompensated HF (exacerbation of symptomatic HF) requiring intravenous diuretics, inotropes, or vasodilators within the last 4 weeks
4. Criterion modified per Amendment 2
 - 4.1. have stage 4 or 5 Chronic Kidney Disease (ie, eGFR < 30 ml/min on dialysis) from the most recent assessment
5. Criterion modified per Amendment 2
 - 5.1. have a history of atraumatic amputation within past 12 months of screening, or an active skin ulcer, osteomyelitis, gangrene, or critical ischemia of the lower extremity within 6 months
6. Criterion modified per Amendment 2
 - 6.1. have a diagnosis of hypotension within 30 days
7. Criterion modified per Amendment 2

-
- 7.1. had major surgery within 3 months or have any surgery, ie, cardiac surgery, planned during the 3-month treatment (except for minor surgery, ie, outpatient surgery under local anesthesia)
 - 8. Criterion modified per Amendment 2
 - 8.1. any condition for which, in the opinion of the investigator, participation would not be in the best interest of the participant (eg, compromise the well-being) or that could prevent, limit, or confound the protocol-specified assessments or have a life expectancy of <6 months or current immobility
 - 9. have known allergies, hypersensitivity, or intolerance to JNJ-28431754 (canagliflozin) or its excipients (refer to Investigator's Brochure, Canagliflozin⁵)
 - 10. be a woman participant who is pregnant, or breastfeeding, or planning to become pregnant while enrolled in this study
 - 11. are legally incompetent
 - 12. Criterion modified per Amendment 2
 - 12.1. currently enrolled in an investigational study receiving an investigational study medication
 - 13. has a left ventricular assist device
 - 14. patient identity or association with enrolling network cannot be verified

NOTE: The required source documentation to support meeting the enrollment criteria are noted in Section 10.2, Appendix 2: Regulatory, Ethical, and Study Oversight Considerations.

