2.3.4. Safety Analysis Set

The safety analysis set includes all randomized participants who received at least 1 dose of study intervention. Summary of available safety data from all sources (claims and patient reported) will be based on this analysis set.

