- Using data from the claims and data on deaths, time to first hospitalization/readmission for heart failure, time to first hospitalization/readmission for other events, and time to death will each be analyzed using a Cox's regression model both for the double-blind treatment period and the entire study duration and include terms for study intervention and stratification factor (HFrEF/HFpEF). Hazard ratios, corresponding 95% CIs, and associated p-values will be presented. Distribution of the times to first hospitalization/readmission for HF, time to first hospitalization/readmission for other events, and time to death will be displayed with Kaplan-Meier curves. Participants who do not experience any such events of interest during the study analysis period will be considered 'censored' in these analyses.

No adjustment for multiplicity will be performed for the exploratory analyses listed above.

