6. SAFETY

Summaries of safety data will be based on the safety analysis set and will use claims data.

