For the prohibited medications, analysis period will include data from the date of informed consent until the end of double-blind treatment period. For all other concomitant medications, analysis period will include data from the date of informed consent until the end of the study. For the HRU data analysis, information collected from date of informed consent until the end of study will be considered in the final analysis.

For both the double-blind treatment period + 30 days after last dose and the 9-month entire study period, descriptive summaries (numbers and percentages) of participants having an SAE/AE of interest will be produced, including by participant's diabetes status (T2DM and non-T2DM) and by randomized intervention group. Discontinuations (and reported reasons) will be summarized by randomized intervention group based on available claims data.

There will be no reconciliation/analysis of SAE/AE data that are self-reported to the Call Center with the data obtained from the claims database.

A listing will be presented for treatment emergent hospitalizations and deaths for each randomized intervention group. AEs occurring between informed consent and the day prior to the first dose of study intervention will also be listed. This listing will be based on participants with informed consent into the study. Depending on the claims/pharmacy data, AEs occurring in participants who used prohibited (commercially available SGLT2is other than the study intervention, canagliflozin) will also be listed.

Based on pharmacy profiles of the participants after-consent in this study, the total number of participants concomitantly receiving UGT inducers during the double-blind treatment period will be summarized combined across both study intervention groups. If the number of such participants is >2% of the total 1,900 targeted for enrollment in this study, the users and non-users of UGT inducers will be summarized by each study intervention group as well and examined further (as

necessary) for any relationship to key study outcomes (eg, PRO endpoints and clinical outcomes reported in claims).

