Appendix 5: CHIEF-HF Study Data Flow Diagram

Step	Description
1A	Health Network sends email to prospective study participants.
1B	Pre-consent Participant clicks link to PRA Patient Experience Website and completes Technology Screening form and contact info submission to "opt in".
1C	PRA Patient Experience opt in triggers Patient ID creation in PRA mHP.
1D	Health Network + VI utilize the PRA mHP Web Application to update Pre-Consent Participant demographic info and assess eligibility.
1E	Care Innovations Zendesk Ticketing System automatically pulls information from PRA mHP for Pre-Consent Participants assessed as "Eligible" and creates an assigned open ticket.
1F	Care Innovations interacts with Zendesk Ticketing System to pick up assigned open tickets.
1G	Care Innovations interacts with PRA mHP Web Application to access Pre-Consent Participant contact information to schedule eConsent call.
2A	Care Innovations initiates communication with Pre-consent Participant to schedule eConsent call and verify contact information (mobile number and address).
2B	Pre-consent Participant interacts with PRA mHP Participant Web Application and Mobile Application to complete pre-consent review.
2C	Care Innovations interacts with VI to coordinate and facilitate completion of eConsent call. Post-consent Participant moves to ePRO completion post eConsent call.
3A	PRA mHP sends questionnaire completion details to SCOUT for payment to participants.
3B	SCOUT sends reloadable payment card and payment to consented participants upon completion of study questionnaires.
3C	PRA mHP interacts with Endpoint IRT at Randomization via a two-way database integration.
3D	PRA mHP interacts with Marken's system via a two-way database integration.
3E	Marken schedules directly with Participant to deliver drug to Participant's home. Care Innovations sends study supplies Welcome Kit to Participant.
3F	During Welcome Call with Care Innovations, Participant is guided through the supplies in the Welcome Kit, which includes the Fitbit watch. Participant interacts with Fitbit Mobile Application for Fitbit set-up and wears Fitbit to collect Biodata / ADL data.
3G	Once authorized within the PRA mHP Mobile Application, Fitbit data is retrieved by PRA mHP automatically through Fitbit API.
4A	PRA mHP sends Symphony encrypted, tokenized PII to match consented Participant in PRA mHP with their available medical claims data in Symphony.
4B	Synoma ID Matches identified in Symphony are sent to DAC

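### Claims-based outcomes have no rule for participants without a claims match, so by default they count as event-free and absolute rates are understated

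*SAP*

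**What the plan says.** **Source.** SAP section 6 states: "Summaries of safety data will be based on the safety analysis set and will use claims data". SAP 5.4.2 takes the counts of intravenous therapies, emergency visits and hospitalisations, and the time-to-first-hospitalisation endpoints, from claims. Protocol 8.3.1 makes claims the only source of serious adverse events once treatment plus 30 days has passed.

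**Linkage.** SAP Appendix 5, step 4A, sends tokenised identifiers "to match consented Participant in PRA mHP with their available medical claims data in Symphony". Step 4B reads: "Synoma ID Matches identified in Symphony are sent to DAC". Only matches found are passed on.

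**Eligibility.** Nothing in protocol 5.1 or 5.2 asks for insurance coverage or a claims match. The nearest criterion excludes a person whose "patient identity or association with enrolling network cannot be verified", which concerns identity and network only.

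**Denominators.** SAP 2.3.4: "The safety analysis set includes all randomized participants who received at least 1 dose of study intervention". On that set, SAP 6.1 says "descriptive summaries (numbers and percentages) of participants having an SAE/AE of interest will be produced". Exploratory endpoints use the FAS (SAP 2.3.2 and Appendix 4), which requires a dose and one post-baseline KCCQ.

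**Censoring.** SAP 5.4.2: "Participants who do not experience any such events of interest during the study analysis period will be considered" censored. No date is attached.

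**Self-reported events.** The texts conflict. SAP 2.3.4 says: "Summary of available safety data from all sources (claims and patient reported) will be based on this analysis set". SAP 6.1 plans call-center events by preferred term for each randomised group. SAP 5.1.2 offers only a possible listing, and protocol 8.3.1 and 9.4.3 also describe a listing.

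**The concern.** A claims feed cannot by itself separate a participant who had no event from one who was never observed. The SAP makes that separation for its other data. A two-week Fitbit interval with more than 7 missing days is set to missing, form-level and item-level KCCQ missingness are distinguished (both in SAP 5.1.2), and time to study termination has an explicit censoring date (SAP 4.2). Claims have no equivalent rule.

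This matters because the trial has no clinic visits, and laboratory tests, vital signs and ECG are marked not applicable in the SAP. Percentages with a serious adverse event or event of interest, resource-use means and cumulative event rates are all planned outputs. If unobserved people sit in the denominator, each of these is too low in both arms, and a safety table looks more reassuring than the true rates would justify.

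**Working it through.** The documents give no figure for matching, so there is none to reproduce. Their main design figure does reproduce (950 per arm, 3 points, SD 18, two-sided 5%: 95.3% power against the stated approximate 95%), but it has no bearing here.

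**Step 1: source against denominator.**

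| Output | Source | Population | Match required |
|---|---|---|---|
| SAE/AE-of-interest percentages (SAP 6.1) | Claims | Safety set | No |
| Hospitalisation, emergency and IV-therapy counts; time to first hospitalisation (SAP 5.4.2) | Claims | FAS | No |
| Time to death (SAP 5.4.2) | Claims and data on deaths | FAS | No |

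A dosed, unmatched participant is in the denominator of the first row and, with one post-baseline KCCQ, of the second, and can contribute no event to either.

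**Step 2: dilution.** Let *m* be the match share (assumed 0.70 to 0.95) and *p* the true risk (10% and 20% as illustrations). Tabulated risk = *m* × *p*.
- 10%: 0.70 × 10% = 7.0%; 0.95 × 10% = 9.5%.
- 20%: 0.70 × 20% = 14%; 0.95 × 20% = 19%.

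With equal *m* in both arms, a risk difference shrinks by the same factor: 4 points becomes 0.70 × 4 = 2.8 to 0.95 × 4 = 3.8. The Kaplan-Meier event rate is also multiplied by *m* if unmatched people are carried to the end of the period, since 1 − [(1 − *m*) + *m*S] = *m*(1 − S). Censoring them earlier dilutes it less.

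**Step 3: people affected.** SAP 1.4 anticipates about 400 to 480 participants. The number without claims is N(1 − *m*): at 95% matched, 20 to 24; at 80%, 80 to 96; at 70%, 120 to 144.

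**Step 4: ratios.** With equal matching, *m* cancels from the risk ratio. For the hazard ratio, treat the unmatched as an event-free fraction that stays at risk, so the apparent hazard in each arm is *m*hS / (1 − *m* + *m*S). Start from 0.67, the hazard ratio for heart-failure hospitalisation quoted in protocol section 2, used only as an illustration.

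| Control risk | *m* = 0.80 | *m* = 0.60 |
|---|---|---|
| 5% | 0.671 | 0.672 |
| 15% | 0.674 | 0.677 |

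The ratio moves materially only if matching differs by arm. The risk ratio is multiplied by *m*(active)/*m*(placebo): 0.75/0.85 = 0.88, or 0.85/0.75 = 1.13 if reversed. At 440 participants and 80% matched, the 95% chance range of the between-arm difference in match share is ±1.96 × √(2 × 0.8 × 0.2/220) = ±7.5 points.

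**Step 5: lost information.** At 440 participants, hazard ratio 0.67 and an assumed 10% control risk, expected events = 220 × *m* × [0.10 + (1 − 0.90^0.67)]. This gives 37.0 at full match, 29.6 at 80% and 22.2 at 60%, with power of 22.9%, 19.2% and 15.5%. No choice of denominator brings these events back.

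**The case against.** **Claims help confirm eligibility, so a match may be implied.** The schedule in protocol 1.3 collects up to 36 months of claims history for that purpose, and protocol 4.1 monitors claims against the entry criteria. This makes widespread non-matching less certain. It is not a requirement: no minimum history is set, Appendix 5 has the network and virtual investigator assess eligibility before consent (step 1D), and past claims do not guarantee coverage over the next 9 months.

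**Claims are not the only by-arm safety source.** A reader might infer from SAP section 6 that they are. SAP 2.3.4 and 6.1 contradict that, so the most that can be said is that claims are the main source and the text conflicts. The gap remains, because SAP 6.1 rules out reconciling the two sources and call-center capture stops 30 days after treatment.

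**The plan never says that unmatched people are event-free or fully followed.** That is right. SAP 5.4.2 gives no censoring date, so complete follow-up cannot be read into it. Event-free status is the default result of the stated denominators, and a programmer could handle these participants differently.

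**Treatment comparisons survive.** Largely so. Linkage failure unrelated to treatment is balanced in expectation, and step 4 shows almost no movement in the hazard ratio. A reader might infer that the Cox results are seriously biased; that would need matching to differ by arm. These analyses are also exploratory, without multiplicity control.

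**Time to death has other sources.** SAP 5.4.2 adds data on deaths, and protocol 7.2 seeks vital status for participants lost to follow-up through the physician or public information as well as claims. It should not be grouped with the claims-only endpoints.

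**Conclusion.** The point holds for absolute claims-based rates. No criterion or analysis set requires a match, and no rule covers a participant without claims or with lapsed claims. The stated denominators therefore give too low an incidence whenever matching is incomplete. At an assumed 70% to 95% matched, every such incidence and risk difference is 0.70 to 0.95 times its true value. The size rests wholly on that assumption. It also supposes that matched and unmatched participants have the same true risk and, for Kaplan-Meier rates, that the unmatched are carried to the end of the period.

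Hazard and risk ratios are little affected under balanced matching, though fewer events are seen. The primary KCCQ analysis is untouched. The SAP should be changed, chiefly for the safety percentages and the hospitalisation and resource-use summaries.

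**What to change.** 1. In SAP 2.3, define two claims-evaluable subsets of participants with a confirmed claims match: one of the safety set, for claims-based AE and SAE tables, and one of the FAS, for resource-use and hospitalisation endpoints. Use them as the primary denominators. Take match status from the token link, not from having a claim during the study, so that membership does not depend on outcome.
2. Report the number matched and unmatched by arm, and keep the all-dosed and full-FAS versions as supplementary tables.
3. In SAP 5.4.2, state the censoring date as the earliest of the end of the analysis period, withdrawal from data collection, death (for non-fatal events) and the end of claims observability. Define the last as coverage end or the data-extract cutoff, whichever is available. It should not be the date of the last claim, because that would censor healthy people with few claims early and inflate event rates.
4. Keep time to death on its separate vital-status sources.
5. Reconcile SAP 2.3.4, 5.1.2, 6 and 6.1 on how self-reported events are reported.

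**Cost.** SAP wording and a flag from the existing match step. Coverage dates are not described in the data flow, so their availability must be checked. Denominators shrink: relative to full matching, intervals for a proportion widen by 1/√*m*, from 1/√0.95 = 1.03 to 1/√0.70 = 1.20 times. The change corrects the rates but does not recover unobserved events.

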6. SAFETY

Summaries of safety data will be based on the safety analysis set and will use claims data.

6.1. Adverse Events

All AE data summaries will be based on the safety analysis set except where stated otherwise. A treatment emergent AE is defined as an event that occurs after the first dose of study intervention (Study Day 1) and/or worsens in severity during the double-blind treatment period.

Adverse events self-reported to the Call Center will be assessed by Janssen Global Medical Safety (GMS) for start and end dates, causality and meeting SUSAR reporting requirements. If the specific dates pertaining to the self-reported AEs are unknown, there will be limited follow-up for resolution. For any events still ongoing at the end of the study, there will be no follow up (as the Call Center will be closed at that point) possible. Adverse events will be coded according to MedDRA and will be reported by preferred term for each randomized intervention group. Janssen Data Management will request a listing of all AEs/SAEs reported to the Call Center from the Janssen GMS. This listing will be shared with PRA (external vendor) to convert the information

into the SDTM format and for inclusion in the final SDTM data package for summary by various subgroups (e.g., T2DM and non-T2DM).

Adverse events collected through the claims database will be analyzed separately for the 12-week treatment period + 30 days after last dose and the 9-month entire study period respectively. It is assumed that claims database will have dates of service provided (procedure dates, office visits, hospital admissions, etc.) but not actual start/end dates of events prior to claims being filed. Therefore, no imputation of AE start/end dates will be feasible based on the claims data. Dates of service(s) rendered to participants during the study (i.e., starting from the time informed consent is signed until the end of double-blind treatment plus 30 days) will be taken into account. The claims data will utilize ICD codes to identify the SAEs and AEs of interest which are defined in the protocol and for the final analysis. The AEs of interest include all severe hypoglycemic events, acute kidney injury, fractures, diabetic ketoacidosis, and lower limb amputation. In addition, hypotension, Fournier's gangrene, genital mycotic infections, urinary tract infections (including urosepsis and pyelonephritis), increased urination and hypersensitivity reactions (including angioedema and anaphylaxis) will be considered for coding and final analysis.

For the prohibited medications, analysis period will include data from the date of informed consent until the end of double-blind treatment period. For all other concomitant medications, analysis period will include data from the date of informed consent until the end of the study. For the HRU data analysis, information collected from date of informed consent until the end of study will be considered in the final analysis.

For both the double-blind treatment period + 30 days after last dose and the 9-month entire study period, descriptive summaries (numbers and percentages) of participants having an SAE/AE of interest will be produced, including by participant's diabetes status (T2DM and non-T2DM) and by randomized intervention group. Discontinuations (and reported reasons) will be summarized by randomized intervention group based on available claims data.

There will be no reconciliation/analysis of SAE/AE data that are self-reported to the Call Center with the data obtained from the claims database.

A listing will be presented for treatment emergent hospitalizations and deaths for each randomized intervention group. AEs occurring between informed consent and the day prior to the first dose of study intervention will also be listed. This listing will be based on participants with informed consent into the study. Depending on the claims/pharmacy data, AEs occurring in participants who used prohibited (commercially available SGLT2is other than the study intervention, canagliflozin) will also be listed.

Based on pharmacy profiles of the participants after-consent in this study, the total number of participants concomitantly receiving UGT inducers during the double-blind treatment period will be summarized combined across both study intervention groups. If the number of such participants is >2% of the total 1,900 targeted for enrollment in this study, the users and non-users of UGT inducers will be summarized by each study intervention group as well and examined further (as

necessary) for any relationship to key study outcomes (eg, PRO endpoints and clinical outcomes reported in claims).

